2.10 Describe your plans for ensuring data security

Once a patient is enrolled they are assigned a unique identification number that is assigned to that patient for the duration of the study. The master database linking the patient name with the unique identification number is stored on one password-protected, secure computer in the Critical Care Research Center. The center is a a locked office with limited accessibility. All paper files are stored in locked cabinets at all times. Research staff are fully trained in the elements of patient privacy and confidentiality.

- 2.11. List the KEY variables that will be collected to support the study aims outlined in item 1.1. KEY variables include those used for:
 - 1) achieving the study aims (outcomes, predictors, potential confounders),
 - 2) identifying the study population (for inclusion/exclusion criteria),
 - 3) describing the study population

Please see an Example of a Completed Table and an Example Data Dictionary.

Variable Name	Data Source (patient survey, EMR, claims, registry)	Purpose (sample identification, description, grouping variable, study endpoint, predictor, covariate)	Measurement Scale (binary, continuous)
Age	EMR/Registry	Description	Continuous
Gender	EMR/Registry	Description	Binary

Percentage of Body Area Burned (%BSAB)	EMR/registry	Description	Continuous
Burn Location(s)	EMR	Description	Descriptive
Presence of Burn Cellulitis	EMR	Confounder	Binary
Post-Burn Day of Stage 1 (Tangential Excision/Integra® Placement with 125 cm² of auto-grafting)	EMR	Covariate	Continuous
Location auto-grafted	EMR	Description	Descriptive
Complications of Integra®	EMR	Covariate	Descriptive
Time to 95% healing of single-stage skin graft	EMR	Study Endpoint	Continuous
Complications of Stage 1 Auto-graft (infection, hematoma, seroma, sloughing)	EMR	Study Endpoint	Descriptive
Post-Burn Day of Stage 2 (auto-grafting remaining Integra areas)	EMR	Covariate	Continuous
Location of control autograft	EMR	Description	Descriptive
Time to 95% healing of control skin graft	EMR	Study Endpoint	Continuous
Complications of control skin graft (infection, hematoma, seroma, sloughing)	EMR	Study Endpoint	Descriptive

2.12 Provide operational definitions of any variables listed above that aren't adequately described by the variable name above, and provide a brief background of any validated measurement scales listed above.

n/a

2.13 If you are collecting data elements besides those listed in Table 2.10 above, provide a justification for gathering the additional data.

Reminder: For chart review studies, a data collection form must be uploaded with your application listing variables collected and how they are recorded (chart review studies). Provided are links to two example chart review tools: **Word Chart Review Example** and **Excel Chart Review Example**

****3. ANALYSIS****

3.1 Describe the statistical methods that will be used to address the study aims. For each aim, this will usually include:

- Description of the sample used for the particular analysis
- The variables included in the specific analysis and their role in the analysis
- Numeric summaries computed (e.g., mean, standard deviation, proportion, correlation)
- A summary of data exploration and presentation activities (e.g., generating scatter plots, summary tables)
- Description of statistical tests (e.g., independent samples t-test, Mann-Whitney test), and models constructed (e.g., logistic regression)

Please see our **Examples of Statistical Methods**.

Describe here:

Note: Please reference the area/pages of an established protocol if you are not writing your own analysis plan.

This is a descriptive pilot study. Means and standard deviations will be computed to describe continuous variables and percents for binary or categorical variables. Patient demographics (age, sex) will be tabulated to characterize the population.

Aim 1 will be to describe the time to 95% healing of the single-stage reconstructed skin graft as well as to determine the frequency of complications of infection, seroma, hematoma, sloughing, and graft loss. Aim 2 will be to compare that to the same characteristics of the adjacent (control) 125 cm² skin graft.

Frequency charts for incidences of complications between the single-stage and control skin grafts will be compared with chi-square tests. Times to 95% healing will be compared with t-tests.

Sample size:

3.2 What is the estimated sample size(s) for the primary study analyses (per group for studies with different arms or comparison groups)?

We plan to evaluate this procedure in 10 patients.

3.3 The sample size selected was (check all that apply):

	Based on data likely to be available during a specific time period (often based on data available in past periods)
	To conduct one or more specific analyses with adequate statistical power
	To achieve a specified level of precision in one or more key estimates
x	Other (explain): This is a descriptive study

3.4 Explain your choice of the sample size selection you listed above:

This is a pilot study – we believe we can enroll 10 patients in a 6 month timeframe and present our results at a regional and/or national conference to proceed with a multi-institutional study.

3.5 Describe your assumptions concerning data available for analysis (e.g. How many subjects will be randomized, possibly lost to follow-up or a procedure? What do you expect for survey response rates, and how much missing data do you expect?). Include information as it pertains to your study (human or animal).

We don't believe any patients will be lost to follow-up, as we will be excluding patients based on this limitation. We expect to have sufficient follow-up data on at least 90% of patients as our post-surgical clinic follow-up rates are above 90%.

Power analysis

NOTE: If you are doing a descriptive study (i.e., aside from computing confidence intervals you are not using statistical tests, inferential statistical testing for group comparisons, or statistical models), please complete 3.6 and skip 3.7-3.8.

If you are conducting statistical tests, using statistical inference to compare groups, or are building statistical models, please skip 3.6 and complete 3.7-3.8. **Please see our Example Power Analysis**.

3.6 Provide a measure of the precision of your estimates for key study endpoints, (e.g., 95% confidence intervals on proportions or means), using actual expected estimates.

This study will be descriptive.

We believe that there will be no increase in graft loss or delayed time to healing, but do not have a precision measure of this information. Our results will be precisely described our findings.

- 3.7 What level of differences observed in your primary endpoints would be considered clinically or practically significant?
- 3.8 What is the power for your primary analysis (and the set of assumptions underlying it: hypothesis addressed, expected pattern of effects with justification for these expectations, analysis used, variables in the analysis, effect sizes, sample sizes, alpha level, one or two-sided test)?

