****MAIN RESEARCH QUESTIONS, STUDY AIMS, SPECIFIC HYPOTHESES****

1.1 Please clearly state your overall research questions and/or study aims.

Primary Research Question:

Does combining the use of Integra®, a synthetic dermal substitute, with the application of a skin graft, known as autografting, into a one-stage procedure result in comparable outcomes to the standard two-stage procedure, so as to be a feasible, safe alternative to the standard two-stage approach?

Primary Hypothesis:

Single-stage Integra reconstruction is safe, i.e. does not result in increased infections, and effective, i.e. does not result in increased graft loss, justifying further study in small to intermediate-sized burns that could result in significantly reduced hospital stays in a specific burn population.

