Post-operatively, the patient's care would be largely unchanged. Progress of graft "take" at the single-stage 125cm² site would be monitored regularly. Eventually, 10-14 days later, the patient would return to the operating room for eventual auto-grafting over their standard Integra®. If autograft "take" at the single-stage site was poor, the area would be regrafted. If graft "take" at the single-stage site was adequate, the area would not require additional surgery. Thus, the total number of surgeries would not be expected to change, as the patient will require two trips to the operating room regardless of trial enrollment. The 125 cm² site would be monitored daily after dressing "take-down" (typically post-operative day 5) while hospitalized and then on a standard post-operative schedule for sloughing or graft loss, infection, hematoma or underlying blood collection, seroma or underlying fluid collection, and time to 95% healed. This last variable is measured by determining the post-operative day at which 95% of the surface area of the graft is covered with epidermis. Because we are meshing the 40 cm² sheet of skin in a 3:1 fashion, the resultant graft will look like a thin fence of skin with open diamond-shaped interstices that will slowly each fill in from the peripheral surrounding skin as the graft heals. It is these interstices that give the typical meshed appearance of healed skin grafts. When 95% of the open areas have filled in, that day is determined to be the time to 95% healing. Similarly, an adjacent area of identical size, which will be treated in the standard fashion, will be monitored serially and will serve as a control. Since patients will serve as their own controls, a direct comparison between reconstruction strategies will be enabled.

Not Applicable

Eligible patients will be adults (Age 18 or older) admitted to the Regions Hospital Burn Center with thermal burns that will be reconstructed with Integra®. There is not a firm protocol in place for Integra® use – this is decided at the level of the burn attending physician on a case-by-case basis.

2.3 What is the study population of interest and what are the study inclusion/exclusion criteria?

Inclusion criteria – English-speaking adult burn patients greater than 18 years old, admitted with burn injuries eligible for Integra® reconstruction at the discretion of the burn attending physicians.

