Enrolled patients will undergo a single-stage reconstruction of 125 cm² of their burn – thin Integra® will be placed with an immediate split-thickness skin graft placed at the time of the first surgery. The remainder of their injury will be treated

according to the routine standard of care – first-stage excision and Integra® placement with second-stage autografting 10-14 days later.

2.8 Provide a brief, sequential, bullet-point description of the all the data collection activities you will conduct from start to finish (e.g., chart review, patient survey, follow-up visits, data pull from the electronic medical record, etc.) and who will conduct each. Please see our Example of Data Collection Steps.

After enrollment, we will collect

- -Age, gender, %BSAB, mechanism of injury, location of burns
- -presence of burn cellulitis
- -Post-burn day of Stage 1 of reconstruction (excision, Integra® placement, and 125 cm² auto-graft)
- -location of 125cm² single-stage reconstruction site
- -percentage of graft coverage at first dressing takedown, typically post-operative day 5 and then daily
- -post-burn day of Stage 2 of reconstruction (auto-grafting over remaining Integra®, re-grafting of initial 125 cm² study area if necessary.
- -time to 95% healing of single-stage grafted area and time to 95% healing of control 125 cm² wound auto-grafted during second reconstruction procedure adjacent to the single-stage graft.
- -single-stage graft site complications (infection, hematoma, seroma, sloughing of graft)
- -adjacent (control) wound complications (infection, hematoma, seroma, sloughing of graft)

2.9 Provide a timeline for the main study activities. Please see our **Example Timeline**

October, 2016 - IRB submission

December, 2016 – February, 2016 – patient enrollment

March, 2016 - April, 2016 - Data Collection/Analysis

May, 2016 – June, 2016 – Abstract/Manuscript preparation

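### Complications at two sites in the same patient are compared with a chi-square test that ignores the pairing

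*Combined protocol and SAP*

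**What the plan says.** Section 2.1 defines the control as a second site in the same patient: "an adjacent area of identical size, which will be treated in the standard fashion, will be monitored serially and will serve as a control". It gives the reason: "Since patients will serve as their own controls, a direct comparison between reconstruction strategies will be enabled". Section 3.2 plans 10 patients, so there are 10 pairs and 20 sites.

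In Section 3.1, Aim 1 describes time to 95% healing and the "frequency of complications of infection, seroma, hematoma, sloughing, and graft loss" at the single-stage site. Aim 2 compares these with the adjacent control. The methods are two sentences: "Frequency charts for incidences of complications between the single-stage and control skin grafts will be compared with chi-square tests", and "Times to 95% healing will be compared with t-tests". Neither mentions pairing, and no other section names McNemar's test, an exact test or a within-patient estimate.

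The complications bear on the primary hypothesis in Section 1.1, that the single-stage procedure "does not result in increased infections, and effective, i.e. does not result in increased graft loss". Sections 2.8 and 2.11 list infection, hematoma, seroma and sloughing separately for each site; Section 2.11 gives their measurement scale as descriptive. Graft loss is not in those complication lists, although Section 2.1 monitors it together with sloughing.

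**The concern.** The Pearson chi-square test assumes independent units. Here each patient contributes one unit to each group, and the two sites share the same patient, the same burn and adjacent wound beds. The test depends only on the two totals. It therefore cannot distinguish complications that fall on both sites of the same patient from complications confined to one site, which is the information the own-control design was set up to give.

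The sample is also too small for the large-sample approximation. With 10 sites per group, one expected count is below 5 unless exactly 10 of the 20 sites have the event.

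The hypothesis is one of no increase in infection or graft loss. A test that rarely rejects does not help such a claim, because non-significance is the likely result whether or not the claim is true. No section says that a non-significant result will be read as safety, but none rules it out, and Section 3.9 makes a multi-institutional study depend on the procedure being judged safe and effective.

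**Working it through.** **Inputs.** From the documents: 10 pairs (3.2), control site within the same patient (2.1), chi-square and t-tests (3.1), and at least 90% of patients with sufficient follow-up, that is 9 pairs (3.5). The plan states no complication rate, correlation, alpha or power (3.6 declines a precision figure; 3.7 and 3.8 are blank), so there is no figure of its own to reproduce. Assumed: two-sided 0.05, risk per site 0.1 to 0.5, within-patient correlation phi 0 to 0.5.

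**Notation.** Of *n* = 10 patients, *b* have the event at the single-stage site only and *c* at the control site only; *x* and *y* are the site totals. The joint probability is p11 = p1·p2 + phi·√[p1(1−p1)p2(1−p2)]. All outcomes of the four-cell multinomial were enumerated exactly, with rejection at p ≤ 0.05.

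**Expected counts.** The expected number of events per group is (x+y)/2 and of non-events (20−x−y)/2. Both reach 5 only if x+y = 10. At equal risks of 0.1 to 0.5, the chance of an expected count below 5 is at least 0.82.

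**Type I error of the uncorrected chi-square test**

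| Risk at both sites | phi 0 | phi 0.25 | phi 0.5 |
|---|---|---|---|
| 0.1 | 0.0090 | 0.0033 | 0.0007 |
| 0.2 | 0.0299 | 0.0125 | 0.0032 |
| 0.3 | 0.0371 | 0.0170 | 0.0046 |
| 0.5 | 0.0422 | 0.0194 | 0.0051 |

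The test is conservative, increasingly so as the correlation rises.

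**Power**

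| Risks | phi | Chi-square | Large-sample McNemar | Exact McNemar |
|---|---|---|---|---|
| 0.5 vs 0.1 | 0 | 47% | 49% | 19% |
| 0.5 vs 0.1 | 0.1 | 47% | 53% | 19% |
| 0.5 vs 0.1 | 0.3 | 45% | 61% | 17% |
| 0.3 vs 0.1 | 0 | 14% | 16% | 2% |
| 0.3 vs 0.1 | 0.3 | 10% | 14% | 1% |

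At 0.5 vs 0.1, phi cannot exceed (0.1 − 0.05)/√(0.25 × 0.09) = 0.05/0.15 = 0.33, so the 61% lies near the limit.

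**Same totals, different pairing.** For 5/10 vs 1/10, chi-square = 20(5·9 − 1·5)²/(10·10·6·14) = 32000/8400 = 3.81, p = 0.051, whatever the pairing. The paired difference is (b−c)/n = +40 points either way. Its 95% score (Tango) interval comes from solving (b−c−nΔ)/√{n[2q + Δ(1−Δ)]} = ±1.96 for Δ, with q the control-only probability estimated under Δ:

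- discordant pairs 4-0 (one patient has the event at both sites): 1 to 69 points;
- discordant pairs 5-1 (no patient has it at both): -9 to 72 points.

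**Sparse table.** For 4/10 vs 0/10, chi-square = 20(4·10)²/(10·10·4·16) = 5.0, p = 0.025. Fisher's exact test gives 0.087 and exact McNemar 0.125. A single sparse table can therefore err towards significance, mainly because the test is not exact rather than because it is unpaired.

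**No events at all.** 0/10 vs 0/10 still leaves a paired score interval of -28 to +28 points.

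**Healing time, if the t-test were unpaired.** 95% half-widths in SD units:

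- unpaired: t(18)·√(2/10) = 2.101 × 0.447 = 0.94;
- paired: t(9)·√[2(1−rho)/10], with t(9) = 2.262, = 1.01, 0.88 and 0.72 at rho 0, 0.25 and 0.5;
- break-even rho = 1 − (2.101/2.262)² = 0.14;
- with 9 pairs: 1.00 unpaired, 0.77 paired at rho 0.5.

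**The case against.** The other side does not dispute the pairing; it argues about weight.

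- **Pilot status.** The study calls itself descriptive, its sample size rests on feasibility, it sets no alpha or decision rule, and Section 3.9 concedes the limits of 10 patients. Per-site data would allow a paired analysis later. This stands and limits the severity. It does not remove the point: Section 3.1 plans significance tests, and the form's own note before 3.6 reserves the descriptive route for studies without them.
- **Charitable reading.** McNemar's test is itself a chi-square test, and the t-tests may be meant as paired. Both are possible. For complications it is the weaker reading, because 3.1 speaks of incidences in two sets of grafts. One sentence would settle each.
- **Little gain in power, and a weaker exact test.** This is correct. At low correlation pairing adds a few points of power at most. Exact McNemar has type I error of only 0.005 and 0.009 at risks 0.3 and 0.5 (phi 0), and needs at least 6 discordant pairs for p ≤ 0.05. The benefit lies in the paired table and interval, so the p-value should be secondary at most.
- **Graft loss.** Section 2.1 monitors sloughing or graft loss as one item, and 2.8 records percentage graft coverage. What remains is labelling: 3.1 counts the two separately, while the complication lists in 2.8 and 2.11 name only sloughing.
- **Healing time.** Naming a paired t-test does not settle which operation starts the clock for each site, or how a regrafted site is counted. That is true, and it is a separate matter for the plan to define.

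**Conclusion.** The concern holds. The complication analysis in Section 3.1 does not match the paired design in Section 2.1, and its approximation is unsuitable for 10 sites per group. It should be fixed, but the consequence is minor to moderate. With zero or positive within-patient correlation the chi-square test is mainly conservative (type I error 0.001 to 0.042 over the assumed range), although single sparse tables can go the other way. The substantive loss is that the reported comparison would not show the discordant patients or an interval for the within-patient difference. All risks, correlations and the 0.05 level are assumptions, since the documents give none. The mismatch itself needs no assumption. The t-test point is a request for clarification only.

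**What to change.** In Section 3.1, replace the two test sentences with:

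> Each complication will be shown as a paired 2x2 table with the discordant pairs and the paired risk difference with its 95% score (Tango) confidence interval, noted as approximate at n = 10; an exact McNemar p-value will be secondary. A non-significant p-value will not be read as evidence of safety. Times to 95% healing will be compared within patients by the mean difference with 95% confidence interval from a paired t-test.

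In Sections 2.8 and 2.11, record each complication as yes/no per site, and either add graft loss per site or state that sloughing covers it.

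**Cost.** Three sentences, yes/no coding, and one item or sentence for graft loss; no extra patients, visits or procedures.

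**Limits to accept.** The score interval is a large-sample method. Its exact coverage at n = 10 is 94.7% to 99.9% over 470 scenarios (risks 0.1 to 0.5, phi 0 to 0.5), so it is usable with the caveat. It can still disagree with the exact test: at discordant counts 4-0, 5-0 and 7-1 it excludes zero while exact McNemar gives 0.125, 0.0625 and 0.070. The estimate and interval should therefore lead.

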3.9 What are the limitations of the proposed approach and analysis?

The limitations are precisely that this is a descriptive pilot study based on a total of 10 patients. While we will characterize our data accurately, this will not be a large enough study, nor will we be auto-grafting a large enough area to extrapolate single-stage reconstruction of large burns. However, should the procedure be deemed safe and effective, it would serve as a springboard to a multi-institutional study involving single-stage reconstruction of small burns, with the definition of "small" to be determined.

3.10 Please name the people who completed the analysis section of this application.

[name]

3.11 Please name the people who will summarize data and conduct statistical analysis.

[name]

****5. DISSEMINATION****

5.1 What are your plans for publication, including target journals?

Journal of Burn Care and Research

Burns

5.2 What plans do you have to share results or translate results to care delivery at HP or for HP personnel?

This is a pilot study. The results will be discussed at a burn conference as well as, ideally, at the American Burn Association annual meeting as well as the Midwest Regional Burn meeting.

****6. ENVIRONMENT****

6.1 Where will the study be conducted? Why is the proposed location appropriate for study?

The study will be conducted at the Regions Hospital Burn Center, where patients are treated.

6.2 How will the results of this study impact the health of HealthPartners members and the community? Be specific as to whether and how you see any clinical application as a result of this study.

This could lead to changes that eventually affect standard of care of a not insignificant portion of burn patients, decreasing costs and shortening hospital stays while maintaining safety and effective clinical outcomes.

6.3 Does the treatment strategy (drug or service) proposed in the study commit HP to covering or continuing to provide the treatment or program support after the study is completed?

No

****7. OTHER REVIEW****

7.1 Has this study been submitted for other review and/or received approval/rejection previously, including but not limited to: Federal, collaborative agency, previous HealthPartners (rejected), or other funding sources (e.g., nonprofit foundation review)?

X	No
	Yes (Provide dates of submission and status of review [approved, pending, or rejected])

